## **STATISTICAL TREATMENT**

Results will be presented as mean  $\pm$  standard deviation. The distribution of normality and homogeneity parameters will be verified using the Shapiro-Wilk and Levene test respectively. Comparison of pre-training values between groups will be analyzed using one-way Analysis of Variance (ANOVA), regardless of data distribution, as ANOVA is robust enough for this (Sawyers, 2013). The effects of training will be evaluated using two-way ANOVA (time x group). If time x group interaction is observed, an analysis will be performed using one-way ANOVA with Tukey's post hoc test for group factor and repeated measures ANOVA for time factor. Significance will be accepted when  $p \leq 0.05$ . All statistical analyzes will be performed using SPSS software (version 25.0). The eta-square values will be used to analyze the effect size: small ( $\eta^2 \geq 0.02$ ), medium ( $\eta^2 \geq 0.13$ ) or large effect size ( $\eta^2 \geq 0.26$ ) (COHEN, 1988). Individuals who do not complete the study will be analyzed using intention to treat. All assessments and data analysis will be performed by researchers blinded to the group of participants.

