## OBJECTIVES

The general objective of this randomized controlled clinical trial is to identify and compare the impacts of traditional concurrent training and concurrent training consisting of strength training combined with dance classes on functional performance, cognitive function and quality of life in older people.

The specific objectives of this randomized controlled clinical trial is to identify and compare the impacts of traditional concurrent training and concurrent training consisting of strength training combined with dance classes on:

- Dynamic balance
- Static balance
- Seat and stand capacity
- Climb stairs capacity
- Lower limb strength
- Hand grip strength
- Muscle thickness of quadriceps
- Specific tension of quadriceps
- Cardiorespiratory capacity
- Quality of life
- Cognitive performance
- Affectivity with the intervention
- Lipid profile
- Depressive symptoms

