## **Sample size**

The sample calculation was performed based on the study by Rodrigues-Krause *et al.*, (2018) for the gait ability variable (TUG) (total n = 27, i.e. n = 9 individuals per group). The calculation was performed using the GPOWER version 3.1.9.4 program, in which  $\alpha = 0.05$  and power of 95% were adopted. Anticipating possible sample losses, three more individuals will be added to each group (total n = 36).

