## **Experimental design**

Initially, an interview will be carried out via telephone (or in person for volunteers who do not have access to this means of communication), in which clarifications about the study will be carried out, as well as scheduling of the first visit. The first face-to-face visit will take place at the University, in which the participants will be introduced to the responsible research subjects, will receive the informed consent form and, if they agree with all the study procedures, will be invited to sign the term in two copies. In case of acceptance, the tests referring to the inclusion criteria will be applied (Baecke's Physical Activity Questionnaire, Mini Mental State Examination and Geriatric Depression Scale), as well the socioeconomic and quality of life questionnaires. If the volunteers reach the required score, respectively below 9.11 and above 24, the second visit will be scheduled. On the second visit, blood collection will be performed to assess the lipid profile.

Afterwards, the subjects will be scheduled for the third visit, in which the quadriceps muscle thickness and quality assessment, anthropometric assessments, as well as familiarization with the lower limb strength test will be performed. Physical tests will be performed on the fourth visit. After the evaluations, the participants will be randomly allocated to one of the two interventions or the control group. After 8 weeks,

a fifth visit will be held, where the physical tests will be reassessed, as well as the application of the questionnaire on affectivity with the intervention. At the end of the 12 weeks of training, participants will be reassessed on all tests.

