## **Arms and Interventions**

*Traditional concurrent training:* The subjects will perform two sessions per week of traditional concurrent training, consisting of strength training followed by aerobic exercise over 12 weeks, with progressive intensities and training volumes. Each traditional concurrent training session will consist of specific warm-up performed on equipment for upper and lower limbs with a load of less than 30% of the training load. Then the bench press, low row, leg press, extension and knee flexion exercises will be performed. Participants will be instructed to perform the concentric phase of the movement in one second and the eccentric phase in two seconds. After strength training, aerobic training (walking outdoors or on a treadmill) will be performed with intensity based on the adapted BORG effort perception scale (ranged to 0 = minimum effort, to 10 = maximal effort).

*Concurrent training consisting of strength training combined with dance classes:* Each concurrent training session associated with dance classes will consist of the same strength training as the traditional concurrent training group, but the traditional aerobic training will be replaced by a dance class. Each dance class will consist of a 5-minute general warm-up with joint mobility exercises and dynamic stretching. Then the main part will be performed with the elaboration of choreography, lasting approximately 20 minutes. Finally, there will be a 5-minute cool-down with stretching exercises. Classes will be held in four different dance modalities, divided into four modules.

*Control group:* Subjects will be instructed to maintain their usual routine during the study period. After the end of the 12 weeks, the participants in the control group will be able to participate in one of the exercise groups according to their preference. The Control Group is necessary in this study, since some of the variables analyzed still have little evidence of the effects of physical exercise. For this reason, in addition to comparing protocols, it is also interesting to compare the results with a group that will not perform physical exercise.

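### The plan commits to no dance-minus-traditional difference or interval, and tests that comparison only after a significant three-arm interaction; the stated 95% power need not apply to it

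*Combined protocol and SAP*

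**What the plan says.** The Objectives section of the combined protocol and SAP states the aim, general and specific, as to "identify and compare the impacts of traditional concurrent training and concurrent training consisting of strength training combined with dance classes". The Arms and Interventions section presents the control arm as an addition to that: "in addition to comparing protocols, it is also interesting to compare the results with a group that will not perform physical exercise".

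The Statistical Treatment section plans four things that bear on this comparison:

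- Descriptive reporting by arm: "Results will be presented as mean" with its standard deviation.
- A three-arm, time by group ANOVA, with significance at p ≤ 0.05.
- A conditional follow-up: "If time x group interaction is observed, an analysis will be performed using one-way ANOVA with Tukey's post hoc test for group factor".
- An effect size: "The eta-square values will be used to analyze the effect size".

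No section plans a between-arm difference or a confidence interval. The text does not say whether the follow-up one-way ANOVA is run on post-training scores or on change from baseline.

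The Sample size section gives the calculation "for the gait ability variable (TUG) (total n = 27, i.e. n = 9 individuals per group"), with alpha 0.05 "and power of 95% were adopted". It then adds three people per group, for a total of 36. It states no effect size, SD, test family or contrast. Under Experimental design there is also an 8-week visit "where the physical tests will be reassessed", so TUG is measured three times.

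**The concern.** The three-arm interaction does not answer the question in the objectives. It can be significant because the control arm alone differs from two equally effective programmes. It can also be non-significant when the two programmes truly differ. In the second case the plan stops, and the reader has arm means, SDs, the omnibus tests and eta-squared, with no contrast between the programmes and no statement of how precisely it was estimated.

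A non-significant interaction next to a 95% power statement is easily taken to mean that dance works as well as traditional training. Whether the data could support that depends on the width of the interval, which the plan does not commit to reporting. It also depends on whether the 95% refers to this contrast, which the Sample size section does not say.

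**Working it through.** **The plan's own figure.** The arithmetic is right: 3 × 9 = 27 and 3 × (9 + 3) = 36. The 27 cannot be recomputed forward because no effect size, SD, correlation or test is given. Solving backwards, 95% power at N = 27 fits several designs:

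- one-way ANOVA with f = 0.81;
- a pre-post interaction with f = 0.40, assuming a correlation of 0.5 between visits;
- a two-group t test at 9 per arm with d = 1.81.

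So the 95% may or may not refer to the dance-versus-traditional pair.

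**Precision of the contrast.** Inputs: 3 arms; n = 9 or 12 per arm (Sample size); Tukey's procedure (Statistical Treatment). Assumption: normal data with equal variances. Units are SD of whichever variable is analysed.

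- df = 3(n − 1); critical t = q/√2, where q is the 5% studentized range point for three groups; half-width = critical t × √(2/n).
- n = 12: df = 33, q = 3.470, critical t = 2.454; 2.454 × √(2/12) = **1.00 SD**.
- n = 9: df = 24, q = 3.532, critical t = 2.497; 2.497 × √(2/9) = **1.18 SD**.
- Unadjusted: 2.035 × √(2/12) = 0.83 SD and 2.064 × √(2/9) = 0.97 SD.

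**Power of the Tukey contrast before the interaction requirement.** Noncentral t with noncentrality d√(n/2) and the critical values above: 80% power needs d = 1.35 SD at 12 per arm and 1.59 SD at 9 per arm.

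**How often the contrast would not be produced (illustrative).** With two visits, the interaction test is a one-way ANOVA on change. Noncentrality is λ = n Σ(mᵢ − m̄)² / [2(1 − r)], with means in raw-score SD and r the correlation between visits. Neither r nor the pattern of means is in the documents. Take control and traditional equal and dance 1.0 SD away: Σ(mᵢ − m̄)² = 2/3, so at n = 12 and r = 0.5, λ = 12 × (2/3) / 1 = 8.

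| r | Interaction not significant, n = 12 | n = 9 |
|---|---|---|
| 0.3 | 48% | 60% |
| 0.5 | 33% | 47% |
| 0.7 | 11% | 24% |
| 0.8 | 2% | 9% |

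By symmetry, if control alone differs by 1.0 SD and the programmes are identical, the interaction is significant in 67% (r = 0.5) or 89% (r = 0.7) of trials at n = 12.

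**Effect of the interaction requirement on the 80% (illustrative).** Same pattern of means, n = 12, true difference 1.35 SD of the analysed variable, two visits, simulated. Interaction and Tukey are both significant in about 68%, 75% and 80% of trials at r = 0.3, 0.5 and 0.7 if Tukey is applied to post-training scores. The figure stays at about 80% if it is applied to change. With three visits and post-training scores (compound symmetry, 8-week effect between two-thirds and all of the 12-week effect) it is 62–69%, 72–77% and about 79%.

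**If the 95% belongs to the three-arm interaction.** Fix that power at 95% with 9 per arm and apply Tukey to change. The chance of a significant dance-versus-traditional result is then 2% if only control differs (no true difference), 36% if the three means are equally spaced, 86% if only dance differs, and 94% if the two programmes are the extremes with control midway.

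**The case against.** Several points on the other side are fair.

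- *The difference can be had by subtraction.* Arm means and SDs will be reported, so a reader can subtract and, for 12-week scores, build an interval from the arm sizes. This stands as far as it goes. It is not a planned analysis, it leaves the multiplicity adjustment to the reader, and for change scores it fails unless the SD of change is also reported.
- *Tukey after a significant interaction is a coherent, prespecified procedure that covers this pair.* True; the comparison is conditional, not absent. But Tukey's procedure controls the family-wise error without a prior omnibus test, so the condition gives this pair no protection it needs.
- *The cost of the condition depends on assumptions.* This stands. On change scores with two visits it costs almost nothing. On post-training scores the loss is material only at lower correlations, and at r = 0.8 the contrast would be missing in only about 2% of trials at 12 per arm. The percentages that depend on r are illustrations; the half-widths do not depend on r.
- *One SD of change is not one SD of the raw score.* Correct. The SD of change is √(2(1 − r)) raw SD, so the 1.00 SD half-width on change is about 1.19 raw SD at r = 0.3 and 0.78 at r = 0.7. This is a further reason to name the scale.
- *No power error is shown, and no section claims equivalence.* Both correct. The power point is limited to what the section leaves unsaid, and the misreading is a risk, not a statement in the plan.

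**Conclusion.** The concern holds. A comparison named in the objectives has no planned estimate or interval, and its only test depends on a three-arm result that answers a different question. If the interaction is not significant, the plan yields no contrast between the programmes and no measure of its precision.

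The main figure is the Tukey-adjusted 95% half-width: about 1.00 SD with 12 per arm and 1.18 SD with 9, which rests only on equal-variance normal data and the stated group sizes. On the same basis, 80% power for the contrast needs about 1.35 or 1.59 SD. How often the contrast would be lost depends on an unstated correlation, pattern of means and analysis scale; at 12 per arm with a true 1.0 raw-score SD difference in the pattern shown, it runs from 48% (r = 0.3) to 2% (r = 0.8).

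The 95% power need not apply to this contrast, but it cannot be said that it does not. The total of 27 is not shown to be miscalculated. This should be changed: it is cheap, and it alters what the trial can conclude.

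**What to change.** Keep the sample size and amend two sections.

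1. **Statistical Treatment.** Add: *For each outcome in the three-arm analysis, the dance-minus-traditional difference in [12-week score or change from baseline; name one] will be reported with its Tukey-adjusted 95% CI whether or not the time by group interaction is significant. A non-significant result will not be interpreted as equal effectiveness.*

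2. **Sample size.** State the test, effect size and contrast entered in G*Power, and limit the 95% to that test. Add: *Before the interaction requirement, the Tukey dance-versus-traditional contrast has 80% power for a difference of about 1.35 SD (12 per arm analysed) or 1.59 SD (9 per arm) of [the same named variable]; power is no higher, and may be lower, once a significant interaction is required first.*

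The cost is protocol wording, one extra reported interval per outcome, and a less favourable figure stated openly for this contrast. No extra participants or visits are needed.

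### After a significant time x group interaction, the plan states no between-arm contrast of change: the time test compares no arms, and the Tukey test does not say what it is run on

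*Combined protocol and SAP*

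**What the plan says.** The aim in OBJECTIVES is to "identify and compare the impacts of traditional concurrent training" and of strength training combined with dance. Arms and Interventions justifies the no-exercise arm on the ground that "it is also interesting to compare the results with a group that will not perform physical exercise".

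STATISTICAL TREATMENT makes the time x group interaction the main test of training effects. It then adds: "If time x group interaction is observed, an analysis will be performed using one-way ANOVA with Tukey's post hoc test for group factor", and alongside it "repeated measures ANOVA for time factor". One threshold covers everything: "Significance will be accepted when" p is at or below 0.05.

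Four things are not stated:
- whether the one-way ANOVA and Tukey test use change or the values at a visit, and which visit;
- whether the time test is run separately in each arm. That is the natural reading, because the two-way model already contains the pooled time effect and an interaction calls for simple effects, but it is not written;
- whether the time tests are descriptive or count as evidence of a programme's effect;
- which follow-up prevails if the two disagree.

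**The concern.** With three arms, the interaction is an omnibus test. Two equally good programmes against an unchanged control can make it significant, and so can one good programme alone. The follow-up has to tell these cases apart.

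A p-value for change within one arm cannot do that. It uses no control data, and finding one arm significant and the other not is not a test of the difference between them. With 9 to 12 people per arm, two arms with the same true gain will often fall on opposite sides of 0.05. The Tukey test could do the job, but only if it is run on the right quantity. On raw week-12 values it carries all the between-person variation that the change score removes, so it may find no pair even when the interaction is significant. The within-arm tests would then be the only significant follow-up on offer.

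At stake is whether the report can say, on a stated and controlled basis, that each programme works and that dance differs or does not differ from traditional training.

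**Working it through.** **The plan's own figure.** Sample size gives 27 evaluable (9 per group) at alpha 0.05 and "power of 95% were adopted", plus 3 per group: 27 + 9 = 36, which is correct. The 27 cannot be reproduced, because the effect size, SD, visit correlation and test family are not given. It can be inverted under assumptions: two visits, the interaction as the powered test, both programmes with the same gain d (in SDs of change) and control at zero. The noncentrality is λ = n × (2/3) × d². Power of 95% with n = 9 and F on 2 and 24 df needs d of about 1.7 (9 × 2/3 × 1.71² = 17.5).

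**Inputs for the illustration.** Three equal arms and the 0.05 level come from the plan, and n = 12 is 36/3. Assumed: two visits, normal change scores with SD 1, both programmes gaining d, control unchanged.

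**Tests.**
- Interaction: with two visits this equals the one-way F on change, with 2 and 33 df.
- Within-arm time test: t = mean change / (s/√12), with 11 df.
- Tukey on change, dance versus traditional: |difference in mean change| / √(MSW/12), against the studentized range for 3 groups and 33 df.

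**Results** (simulation, at least 100,000 trials per setting):

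| True gain d in both programmes | 0.6 | 0.8 | 1.0 |
|---|---|---|---|
| Power of one within-arm test | 47% | 71% | 88% |
| Interaction significant | 29% | 48% | 67% |
| Exactly one trained arm significant, given an interaction | 55% | 34% | 16% |
| The same, as a share of all trials (product of the two rows above) | 16% | 16% | 11% |
| Tukey on change separates the two arms, given an interaction | 7% | 4% | 3% |

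The two arms are truly equal throughout, so any claimed difference is false. At d = 1.2 the discordance given an interaction is about 5%. At d = 1.7 it is about 0.1% with 12 per arm and about 1% with 9. With the planned 9 evaluable per arm it is 65%, 47% and 30% at d = 0.5, 0.8 and 1.0.

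**If Tukey is run on raw week-12 values.** When the SD of change is 1, the raw SD is 1/√(2(1 − ρ)), where ρ is the correlation between visits. That is 1.00 at ρ = 0.5 and 1.58 at ρ = 0.8, so a gain of 1.0 SD of change is only 1/1.58 = 0.63 raw SDs at ρ = 0.8. For d = 0.6, 0.8 and 1.0, no pair is significant in about 79%, 73% and 64% of trials with an interaction at ρ = 0.8, and in 52%, 37% and 24% at ρ = 0.5. Both correlations are assumptions.

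**The case against.** The strongest reply is that the plan already compares arms. "The effects of training will be evaluated using two-way ANOVA (time x group" names an interaction that contrasts change across all three arms, control included, and the time tests come only after it and together with Tukey. Simple-effects tests after an interaction are a recognised practice. All of this stands, and it rules out saying that the plan relies on uncontrolled change. It does not supply the missing step: the interaction does not identify which arms differ, and Tukey's input is left open.

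A second reply is that the illustrative gains are small for a trial planned at 95% power. At the gain of about 1.7 SD implied above, the discordance nearly vanishes. This too stands for an outcome with such an effect, subject to the unstated test family. But the calculation concerns the Timed Up & Go only, while the same follow-up serves every outcome listed in OBJECTIVES, and the plan gives no basis for expecting so large a gain on each.

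A reader might also infer that learning the tests will pass for a training effect, since the visit schedule mentions practice only for one test ("familiarization with the lower limb strength test will be performed"). The documents do not support that as a finding about the main analysis. Practice shared by all arms cancels in the interaction, which it makes significant only at about the 5% level. Risks and benefits also promises familiarization with the exercises, though it does not clearly cover the functional tests. Shared practice remains only inside a within-arm p-value, which is one more reason not to treat that p-value as evidence.

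**Conclusion.** The point holds as a gap in the follow-up. The main test is sound in kind, but after it no stated contrast says whether each programme beat control or whether dance differed from traditional training. For moderate gains (0.6 to 1.0 SD of change, 12 per arm), the within-arm tests split two equal programmes in 16% to 55% of trials with an interaction, or 11% to 16% of all trials. A Tukey contrast of change does so in 3% to 7% of trials with an interaction. For large gains the problem is negligible. These sizes rest on assumed effects, two visits and normal change scores, and the raw-value figures also on assumed correlations.

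A reader might infer that within-arm p-values will be reported as programme effects. The plan does not say so, and separate testing by arm is itself a natural reading rather than stated text. What can be said is that nothing in the section rules that use out. Nor should the time test be read as a set of uncorrected visit-by-visit comparisons: the plan names an omnibus repeated measures ANOVA.

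**What to change.** Rewrite the follow-up sentence in STATISTICAL TREATMENT to this effect: after a significant interaction, conclusions rest on Tukey-adjusted pairwise between-arm differences in change from baseline (or in baseline-adjusted week-12 values) with 95% confidence intervals, for each programme versus control and for dance versus traditional training. Within-arm change is reported as mean and SD, with no p-value offered as evidence of effect. If change is used, name the visit; week 12 is when all tests are repeated.

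The cost is one or two sentences, with no new participants, visits or measurements. The downside is that within-arm p-values, which some readers in this field expect, are no longer presented as evidence.

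### No primary outcome, time point or contrast is named, and every outcome is tested at p ≤ 0.05 with no rule across 14 unranked objectives

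*Combined protocol and SAP*

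**What the plan says.** All references are to the combined protocol and SAP.

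- **STATISTICAL TREATMENT.** Training effects are assessed by a two-way ANOVA with factors time and group. A significant interaction leads to one-way ANOVA with Tukey's "post hoc test for group factor and repeated measures ANOVA for time factor". On the threshold: "Significance will be accepted when" p is at most 0.05. On magnitude: "The eta-square values will be used to analyze the effect size". The section does not rank outcomes, adjust across them or label any as exploratory. It also does not say how many time levels the ANOVA has.
- **OBJECTIVES.** The general objective covers "functional performance, cognitive function and quality of life in older people". The next sentence begins "The specific objectives of this randomized controlled clinical trial is to identify and compare the impacts" and leads into 14 bullets in no stated order of importance.
- **Sample size.** The calculation was done "for the gait ability variable (TUG"), with alpha 0.05 and 95% power. It gives 27 participants, raised to 36 for losses. TUG is not called primary here or elsewhere.
- **Experimental design.** There is a visit at 8 weeks, "where the physical tests will be reassessed, as well as the application of the questionnaire on affectivity with the intervention". All tests are repeated at 12 weeks.
- **Arms and Interventions.** The control group is justified partly because "some of the variables analyzed still have little evidence of the effects of physical exercise".

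**The concern.** The plan does not say which result the main conclusion rests on. With three domains in the general objective, 14 listed objectives and up to two follow-up times, one interaction below 0.05 is enough to claim a training effect, wherever it appears. A reader of the final report could not tell a conclusion fixed in advance from one picked afterwards.

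Nothing else in the plan fills this gap. Tukey's test controls the group comparisons inside one outcome and does nothing across outcomes. Eta-squared describes the size of an effect; it neither limits false positives nor identifies the deciding result.

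The stake is interpretability. With 36 participants in three arms, the nominal 5% applies to each test taken alone, not to the trial's claim that training had an effect.

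**Working it through.** **1. What the plan's own figures settle.** Sample size gives 27 in total (9 per group) and adds 3 per group: 27 + 3 x 3 = 36, which agrees. The 27 itself cannot be reproduced, because no effect size, SD or type of test is given. Back-solving at 95% power gives an effect size f of about 0.81 if the test was a one-way ANOVA, and 0.23 to 0.57 if it was a group x time interaction (two or three time points, within-person correlation 0 to 0.8). The calculation therefore does not reveal which test, time point or contrast was meant for TUG.

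**2. How many tests.** OBJECTIVES lists 14 items. Affectivity has no baseline measurement in Experimental design and refers to sessions that controls do not attend, so 13 fit a pre/post three-arm test. The number of tests is not fixed, however. Under OUTCOME MEASURES the lipid profile has four components, and lower limb power output appears there without being among the 14 objectives.

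**3. Illustration.** Assume seven truly null tests, about half of the listed objectives. This number is an assumption.

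If the tests are independent, the chance of at least one false finding is 1 − (1 − 0.05)^k. With k = 7: 1 − 0.95^7 = 1 − 0.698 = 0.302.

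If outcomes are correlated, the chance was simulated. With two time points, the interaction F equals the one-way F on change:

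F = (SS between / 2) / (SS within / (N − 3))

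The degrees of freedom are 2 and 33 for N = 36, or 2 and 24 for N = 27. With three time points they are 4 and 66, or 4 and 48. The settings were three equal arms of 9 or 12, normal outcomes with one common correlation, sphericity for three time points, no true effects, and 20,000 runs per setting. The simulation error is about √(0.24 x 0.76 / 20,000) = 0.003.

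| Assumed outcome correlation | Chance of at least one false interaction, 7 nulls (range over arm size and number of time points) |
|---|---|
| 0 | 0.298–0.304 (exact 0.302) |
| 0.3 | 0.278–0.279 |
| 0.5 | 0.238–0.247 |
| 0.8 | 0.157–0.163 |
| 0.9 | 0.118–0.126 |

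Arm size and the number of time points hardly matter. The correlation does. As it approaches 1 the figure falls towards 0.05, so no row is a floor.

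**4. With the fix.** One named primary test at 0.05 has a false-positive chance of 5%, whatever the other outcomes do.

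**The case against.** **TUG is already the implicit primary outcome.** The trial is sized on it alone, so the gap may be one of labelling. This stands in part, and it is why TUG is the natural choice. But the plan never says so, and TUG cannot speak for cognition or quality of life, which the general objective also names. Even if TUG is accepted, the time point and the deciding contrast remain open, and the other outcomes are still tested at 0.05 with no secondary label.

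**The percentages are assumptions.** This stands. The documents give neither the number of true nulls nor any outcome correlation. Some outcomes must be related: specific tension is calculated from knee-extension 1RM and muscle thickness. Independence therefore overstates the risk, and the figures show scale only.

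**Which outcomes are null?** A reader might infer that quality of life, cognition, lipids and depressive symptoms are the null set. The documents do not support that. The Introduction says physical activity can reduce depressive symptoms and slow cognitive decline, and it lists better cognition among the benefits of dance. Arms and Interventions says only that evidence is thin for some variables, and does not name them. A partly null set is plausible; its membership is unknown.

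**Does the planned interaction mix weeks 8 and 12?** A reader might take this as given. STATISTICAL TREATMENT does not state the time levels, so it holds only if the week 8 measurement enters the ANOVA.

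**Conclusion.** The gap is real and should be closed before analysis. The plan designates no primary outcome, time point or contrast, and it applies p ≤ 0.05 to each outcome with no rule across the 14 objectives. That conclusion rests on the text alone and needs no assumed number.

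The size is illustrative. With seven true nulls, the chance of at least one false interaction is about 30% at correlation 0, 24% at 0.5, 16% at 0.8 and 12% at 0.9, that is, roughly 2.4 to 6 times the nominal 5%. It depends on the assumed count of nulls, one common correlation, normal data and sphericity. It should not be read as this trial's known error rate, or as evidence that any given outcome will show no effect.

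**What to change.** In STATISTICAL TREATMENT, before analysis:

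1. Name one primary outcome, one time point and one test, and rest the main conclusion on that result. TUG at week 12 is the natural choice given the sample size section. The investigators should confirm it, because the general objective is wider.
2. State the test, for example a three-group comparison of the change in TUG from baseline to week 12 at 0.05, followed by Tukey. Say in advance which contrast carries the conclusion: dance versus traditional training, or each training arm versus control. Otherwise a difference driven only by training versus control would leave the comparison of the two programmes unresolved.
3. State the time levels of the planned ANOVA. If week 8 is included, its interaction is not a week 12 test, and the primary test must be written separately. If it is pre/post only, its interaction is the same test as the comparison of change.
4. Label all other outcomes and all week 8 results secondary or exploratory, and report them as estimates with 95% confidence intervals. Apply Holm across them only if confirmatory claims are wanted.

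The cost is SAP wording and one decision by the investigators. No visit or measurement changes. The downside is that fewer secondary results can be called significant, and the domains not chosen as primary become secondary.
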